5.3 INCLUSION CRITERIA

A subject will be considered eligible for inclusion in this study only if all of the following criteria apply:

1. Subject has degenerative disc disease (DDD) at one level, from L2 to S1 vertebrae, with up to Grade I spondylolisthesis.

DDD is defined as back pain and/or radicular leg pain with degeneration of the disc confirmed by patient history, radiographic studies, and physical examination, with one or more of the following factors (as measured radiographically, either by CT, MRI or plain film, myelography, discography, *etc.*):

- > osteophyte formation of facet joints or vertebral endplates;
- > decreased disc height, on average by > 2 mm;
- scarring/thickening of ligamentum flavum, annulus fibrosis, or facet joint capsule;
- herniated nucleus pulposus;
- facet joint degeneration/changes;
- vacuum phenomenon.
- 2. Subject is candidate for single level intervertebral fusion, with or without posterolateral fusion, with implantation of intervertebral body fusion device and supplemental fixation.
- 3. Subject age is between 21 72 years, and subject is skeletally mature.

- Pre-operative low back and/or leg/s pain (debilitating pain that causes a significant disturbance of the routine daily physical activities) ≥ 40 mm on a 100 mm Visual Analogue Scale (VAS).
- 5. Pre-operative Oswestry Disability Index (ODI) score \geq 40 percentage-point, indicating at least moderate disability (interpreted as moderate/severe disability).
- 6. Low back and/or leg/s pain is unresponsive to prior non-surgical management for a minimum of six months. Non-operative treatment includes pain medication, physical therapy and/or injections.
- 7. Patient must understand and sign the informed consent.
- 8. Patient is willing and able to meet the proposed follow-up schedule including return to follow-up visits and complete necessary study paperwork.
- 9. Patient is willing and able to follow the postoperative management program.

5.4 EXCLUSION CRITERIA

A subject will not be considered eligible for inclusion in this study if any of the following criteria applies:

- 1. Previous fusion or fusion attempts, including anterior fusion or posterolateral fusion, at the index level.
- 2. Previous fusion or fusion attempts at the adjacent levels.
- 3. Prior decompression procedures that include removal of soft and bone tissue at the index or adjacent levels.
- 4. Patient is not skeletally mature.
- 5. Degenerative spondylolisthesis greater than Grade I.
- 6. Spinal instability at the index level with ≥ 3 mm translation and/or ≥ 5 degrees angulation. Determination of instability will be assessed using flexion/extension lateral view radiographs.
- 7. Isthmic spondylolisthesis.

8. Radiographically confirmed moderate or severe spinal stenosis with associated neurogenic claudication.

Definitions:

- Radiographically confirmed moderate/severe stenosis is defined as reduction of >50% of central and/or foraminal canal diameter compared to the adjacent uninvolved levels.
- Neurogenic claudication is leg, groin, or buttock pain and/or numbness that worsens with walking or erect posture and is relieved with flexion of the spine.
- 9. Systemic infection or infection at the site of surgery.
- 10. Metabolic bone disease, such as osteopenia, osteoporosis, and osteomalacia. A screening Questionnaire for osteoporosis, SCORE (Simple Calculated Osteoporosis Risk Estimation), will be used to screen patients who require a DEXA bone mineral density measurement. If DEXA is required, exclusion will be defined as measured T-score less than or equal to -2.5 (WHO definition).
- 11. History of Paget's disease or other bone pathologies, whether acquired or congenital, including renal osteodystrophy, untreated or uncontrolled hyperthyroidism, hypothyroidism, or hyperparathyroidism, Ehrlers-Danlos-syndrome, osteogenesis imperfecta, achondroplasia, tuberculosis.
- 12. Personal and/or familial history NF2, and/or spinal tumor.
- 13. Ankylosing spondylitis.
- 14. Diffuse idiopathic skeletal hyperostosis (DISH) syndrome.
- 15. Active hepatitis (viral or serum) or HIV positive, renal failure, systemic lupus erythematosus, or any other significant medical conditions which would substantially increase the risk of surgery.
- 16. Immune deficiency disease.
- 17. Patient is receiving immunosuppressive or long-term steroid therapy.
- 18. Active malignancy or other significant medical comorbidities.
- 19. All concomitant diseases that can jeopardize the functioning and success of the patient.

- 20. Allergy to any component of the investigational device, including carbon fiberreinforced polyetheretherketone (CFR-PEEK), titanium, and tantalum.
- 21. Pregnancy, or female subject interested in become pregnant during the duration of the study.
- 22. Current chemical dependency (*e.g.*, drug and/or alcohol abuse, according to DSM-V definition), as well as those with a history of such abuse.
- 23. Uncontrolled depression, psychosis, or other symptoms of a mental disorder that, in the investigator's opinion, likely would make the subject unable to comply with the study procedures and could affect the study outcome.
- 24. Treatment with drugs that may interfere with bone metabolism, such as glucocorticosteroids, calcitonin, bisphosphonates, bone therapeutic doses of fluoride, bone therapeutic doses of vitamin D or vitamin D metabolites, and treatment by chemotherapy.
- 25. Morbid obesity (BMI \ge 40).
- 26. Current smokers (including 3 months prior to surgery).
- 27. Scoliosis, Cobb angle greater than 11°.
- 28. Vertebral fractures.
- 29. Severe muscular, neural or vascular diseases that endanger the spinal column.
- 30. Missing bone structures, due to severely deformed anatomy or congenital anomalies, which make good anchorage of the implant impossible.
- 31. Paralysis.
- 32. Current use of other investigational drug or device.
- 33. The patient is involved in a worker's compensation case or spine-related litigation.
- 34. The patient is a prisoner.
- Note: The time elapses between the diagnostic studies required for entry and enrolment into the study is limited to up to three months.

5.5 NUMBER OF PATIENTS AND PATIENT SELECTION

Patients Number:

A total of 55 patients will be recruited for the study (up to 15 subjects will be recruited in this site). Their results will be combined with an additional 45 patients from the ongoing OUS

study, the details of which are presented in the Investigator Brochure. When combined with the patients from the ongoing OUS study, 55 patients was deemed sufficient for this confirmatory, single-arm study. Therefore, the total effective sample size is about 100 patients.

Patients Selection:

In order to be included in this study, patients will have to fulfill all the Inclusion Criteria and none of the Exclusion Criteria, as well as to sign and date the Informed Consent Form.

All patients' full medical history will be recorded and all patients will undergo a complete general physical and neurological examination. Plain A-P and lateral X-Ray films, as well as lateral flexion-extension X-Rays, will be performed prior to surgery.

Neurological examination will be performed to confirm that the patient' clinical signs and symptoms are consistent with the baseline disease level/s demonstrated per imaging.

An anesthesiologist will assess the patient for general anesthesia, according to the routine practice.

5.6 STUDY SITES

Up to eight sites may participate in the study. At least two sites will be in the USA, recruiting at least 30 patients.

5.7 STUDY DURATION

The study is expected to last up to 36 months (total duration), including patient enrollment and a post-operative follow-up period of 24 months per subject.

The primary safety and effectiveness analyses will be performed at 24 months. The collected information will be submitted to the FDA as part of a 510(k) Premarket Notification after all patients have completed 24 months of follow-up. In case of satisfactory results, the Company intends to submit the results of the study to the FDA, after all patients have completed the 12 months follow-up, as part of a Premarket Notification (510(k)). It is emphasized, that all patients will be additionally followed at 24-month time point, and afterwards annually, until the last patient completed 2-year follow-up. It is noted, that at the time all subjects from IDE

study reach 12-month follow-up, it is expected that 2-year supportive data from the original, ongoing OUS clinical study with the investigational device will be available.

Patients will be followed and assessed both clinically and radiographically after surgery at follow-up visits.

Evaluation time points shall be conducted at the following intervals:

- Preoperatively (with up to 3 months between the diagnostic studies to enrolment);
- Operatively;
- Postoperatively, at discharge from hospital;
- Postoperatively, at 6 weeks \pm 2 weeks from surgery;
- Postoperatively, at 3 months \pm 2 weeks from surgery;
- Postoperatively, at 6 months \pm 1 month from surgery;
- Postoperatively, at 12 months \pm 2 months from surgery.
- Postoperatively, at 24 months \pm 2 months from surgery.

Afterwards, subjects will be clinically evaluated annually, until the last patient has completed 2-year follow-up.

At baseline, discharge, and at follow-up sessions, radiographic evaluation, pain and functionality evaluations, and subject's overall well-being assessment shall be performed. Assessment of subject' satisfaction shall be performed postoperatively, starting at 6-week follow-up.

Complications/adverse events shall be evaluated operatively and at each evaluation time points, as well as throughout the study.

Refer to Sections 5.9 and 5.10 for a detailed schedule and assessment description, respectively.

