5.12 STUDY SUCCESS CRITERIA

The results of the study at 12 months and 24 months postoperatively for all participating subjects will be evaluated, with reference to the reported results from the

literature, as summarized in **Section 5.2.1**. In addition, assessment of success rate will be conducted at each time point, as applicable.

In addition to evaluating individual patient success as the primary composite endpoint, each element of the composite will be evaluated individually as secondary endpoints, as described below.

Fusion – Success for the fusion outcome measure will be defined as two year fusion rate comparable to the two and one year fusion rates presented in the literature. The pooled results of the Company literature research (for patients with DDD treated with pedicle screws with PLIF/ALIF/TLIF and/or PLF), as presented in **Section 5.2.1**, demonstrated at 12 and 24 months postoperatively fusion rates in the different studies ranging from 77% to 97%.

As discussed in **Section 5.2.1.A**, the weighted average for the fusion rate of the ten articles is 87.79%. Based on the literature, we believe our fusion rate will be 88%.

The assumed fusion rate of 88% has a 95% confidence interval of $\pm 6.4\%$ for 100 patients. Notably, the lower bound of this confidence interval, 81.6%, is within the range of the fusion rates reported in the selected literature.

Safety – Success with regard to safety outcome measure is defined as no worsening in neurological status (motor, sensory, reflex, straight leg raising, and tenderness assessments) and no new permanent neurological deficits (present for at least 2 successive visits at or beyond 6 months), absence of device-related serious adverse events, and absence subsequent surgical interventions at the index level, through 24 months, comparable to neurological deficit, device-related serious adverse events, and subsequent surgical interventions rates presented in the literature.

Based on the literature review in FDA's Executive Summary, the rate of these events in the literature control is 13.5%.

Therefore, the Company estimates that the adverse event rate for these events will be 13.5%. With a sample size of 100 patients, this adverse event rate has a 95% confidence interval of $\pm 6.7\%$.

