As indicated above, it is believed that at the time all subjects from the IDE study complete one year follow-up, supporting safety data for 24 months will be available for about 45 patients from the ongoing, OUS study.

**Pain - Individual patient, clinically meaningful, improvement with respect to pain is defined as postoperative improvement at 24 months of at least 20 mm on a 100 mm VAS from the baseline level.**

Value of 73% of patients with \geq 20 mm improvement. This value is selected as it is consistent with the performance of the Silhouette Spinal Fixation System reported in P070031.

Function - Individual patient, clinically meaningful, improvement with respect to function is defined as postoperative improvement at 24 months of at least 15 points on the ODI graded on a 100-point scale as compared to baseline assessment.

Value of 55% of patients with \geq 15 points improvement. This value is selected as it is consistent with the performance of the control group reported in P050010.

Individual Patient Success (Overall Success)

Individual patient success (*i.e.*, overall success) will be determined at 24 months and is defined as a composite primary endpoint. An individual subject will considered a success if all of the following criteria are met:

- Presence of continuous bridging bone between the involved motion segment at 24 months, *i.e.*:
 - Presence of interbody bridging bone and absence of radiolucency > 50%; OR
 - Presence of left posterolateral bridging bone; OR
 - Presence of left posterolateral bridging bone.
- No motion on flexion/extension films at 24 months (success is defined as angular motion < 3° and translational motion < 3 mm);

- Improvement of at least 20 mm on a 100 mm VAS from baseline level at 24 months;
- Improvement of at least 15 points on the ODI graded on a 100 point scale at 24 months as compared to baseline;
- ➢ No worsening in neurological status (motor, sensory, reflex, straight leg raising, and tenderness assessments) and no new permanent neurological

deficits present for at least 2 successive visits at or beyond 6 months (out to 24 months);

- > Absence of device-related serious adverse events through 24 months;
- Absence of subsequent surgical interventions at the index level through 24 months.

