The study will be considered a success if the overall success rate for the CarboClear Device is 41%. This value is selected as it is consistent with the performance of the control groups reported in P050010 and P070031.

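### Section 5.7 fixes the primary analysis and submission at 24 months, then lets undefined satisfactory results trigger submission at 12 months, where no success rule exists

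*Combined protocol and SAP*

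**What the plan says.** Section 5.7 (Study Duration) makes four statements in sequence:

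- On the primary analyses: "The primary safety and effectiveness analyses will be performed at 24 months".
- On the default timing of submission: "The collected information will be submitted to the FDA as part of a 510(k) Premarket Notification after all patients have completed 24 months of follow-up".
- On the early option, given "satisfactory results, the Company intends to submit the results of the study to the FDA, after all patients have completed the 12 months follow-up".
- On what happens after an early filing: "It is emphasized, that all patients will be additionally followed at 24-month time point", with yearly visits after that until the last patient reaches two years.

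It adds that two-year data from the ongoing study outside the US (OUS) should be available when the IDE patients reach 12 months.

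Section 5.12 (Study Success Criteria) opens with "The results of the study at 12 months and 24 months postoperatively for all participating subjects will be evaluated", the comparison being with the literature, and adds a success-rate assessment at each timepoint as applicable. Overall success, however, "will be determined at 24 months and is defined as a composite primary endpoint". The pass rule is attached to that composite: "The study will be considered a success if the overall success rate for the CarboClear Device is 41" percent. Pain and function success are defined at 24 months. Section 5.10.3 defines freedom from device-related serious adverse events and from index-level surgery through 24 months. In contrast, Section 5.2.1.A describes fusion with the study device as assessed at one year.

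Section 5.2 calls the study confirmatory and its statistical analyses descriptive. No alpha, power or rule covering two timepoints is given.

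**The concern.** The second and third statements in Section 5.7 cannot both stand as the plan for submission. What chooses between them is the result itself, against a standard that is not written down. Nothing says which endpoint must look satisfactory, at what level, or who decides. The study is single-arm, and Section 5.12 has success rates assessed along the way, so the sponsor will know the 12-month figures when it chooses.

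Two things are at stake. First, a favourable chance fluctuation at 12 months can be put forward, while an unfavourable one simply leads to waiting for 24 months. A bare point-estimate bar with no confidence bound is easily affected by such a choice. Second, the safety components accumulate over 24 months, so a 12-month count is incomplete. The neurological criterion concerns deficits present at two successive visits at or beyond 6 months. At 12 months only the 6- and 12-month pair exists, and a deficit first seen at 12 months cannot be confirmed until 24 months.

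**Working it through.** **The plan's own figures.** Section 5.12 gives 95% half-widths for 100 patients, and both reproduce:

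- Fusion: 1.96 × √(0.88 × 0.12 / 100) = 6.37 points (stated 6.4).
- Safety: 1.96 × √(0.135 × 0.865 / 100) = 6.70 points (stated 6.7).

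The documents give no operating characteristics for the 12- and 24-month evaluations, so the next step is an illustration.

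**Crossing 41% at one time or at either time.** From the documents: n = 100 (55 IDE plus about 45 OUS, Section 5.13.1) and a 41% bar, read as 41 or more successes. Assumed: the same true rate p at both times, the bar applied at both, and a latent-normal correlation ρ of 0.5 to 0.85 within patient.

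One look: P(X ≥ 41), with X binomial(100, p).

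Either look: 1 − P(X₁₂ ≤ 40 and X₂₄ ≤ 40). Let p₁₁ be the chance that a patient succeeds at both times. Given X₁₂ = x, X₂₄ is the sum of binomial(x, p₁₁/p) and binomial(100 − x, (p − p₁₁)/(1 − p)). At p = 35%, p₁₁ is 0.196, 0.233 and 0.268 for ρ = 0.5, 0.7 and 0.85.

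The last column holds the 45 OUS outcomes fixed at their 24-month values for both looks, so that only the 55 IDE outcomes can change.

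| True rate | 24 months only | Either time, all 100 can change | Either time, OUS fixed |
|---|---|---|---|
| 35% | 12.5% | 19.3–21.7% | 17.6–19.4% |
| 38% | 30.1% | 42.1–46.9% | 38.8–42.3% |
| 41% | 53.8% | 67.5–73.3% | 63.8–67.8% |

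**Safety follow-up at a 12-month submission.**

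- IDE patients, guaranteed: 55 × 1 = 55 of 55 × 2 = 110 patient-years, or 50%.
- Pooled, if the OUS patients have 24 months: (55 + 45 × 2) / 200 = 145/200 = 72.5%.
- A total duration of 36 months with 24 months of follow-up implies about 12 months of enrolment. If enrolment is uniform and all data up to the cut are used, mean IDE follow-up is 18 of 24 months (75%), and the pooled figure is (55 × 1.5 + 90) / 200 = 86%.

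**The 13.5% safety comparator.** Section 5.2.1.D gives it no time window. Assume that it is a 24-month rate with constant hazard:

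- 12-month equivalent: 1 − √(1 − 0.135) = 7.0%. In 55 patients that is 3.8 expected failures, against 55 × 0.135 = 7.4 at 24 months.
- Pooled set with IDE at 12 months and OUS at 24: 0.55 × 7.0% + 0.45 × 13.5% = 9.9%. The ratio 13.5/9.9 is about 1.4.

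**The case against.** Section 5.7 governs when data are filed, not when success is declared. The primary analyses stay at 24 months, every patient is followed to 24 months whatever is filed, and the 41% rule belongs to the 24-month composite. This is correct, and it rules out several stronger readings that a reader might infer:

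- **That the trial formally tests its success criterion twice and inflates its error rate.** No 12-month version of the 41% rule is written, and there is no alpha to inflate. The first opportunity is against an unstated standard.
- **That the whole analysis would rest on half the safety exposure.** This fits only the guaranteed follow-up of the 55 IDE patients. For the 100-patient set the figure is about 72.5% or more. The OUS patients are only a partial substitute, since Section 5.13.1 says that they received no interbody device.
- **That a 12-month safety comparison flatters the device twofold.** Under the stated assumptions that is roughly right for IDE patients alone (13.5% against 7.0%). It falls to about 1.4-fold if the OUS patients contribute 24-month data.
- **That 12-month IDE and 24-month OUS outcomes will be merged into one rate.** The plan calls the OUS two-year data supportive and does not say which OUS timepoint is pooled. OUS patients also have a 12-month visit.

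The equal-rate assumption is also open to challenge. Section 5.2.1.A expects slightly lower fusion at one year, which works against an early pass, while cumulative safety failures would be fewer at 12 months, which works in its favour.

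What remains is the contradiction in Section 5.7, the outcome-dependent trigger and the absence of any 12-month criterion. Calling the analyses descriptive does not remove these from a study that is also called confirmatory and has a pass rule.

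**Conclusion.** The point holds. As written, the timepoint at which the study is first put forward depends on the observed result, and a 12-month submission would rest on endpoints that the plan defines only at or through 24 months. The 24-month analysis is pre-empted for submission, not removed.

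The size is moderate and illustrative. If the same bar were used at either time, a device with a true rate of 35% would reach it about 18–22% of the time instead of 12.5%, and one at 41% about 64–73% instead of 54%. These figures rest on the assumed equal rates and correlations. The direction is secure under those assumptions; the exact size is not. The safety figures of 7.0% and 9.9% hold only if 13.5% is a 24-month rate with constant hazard, which the documents do not say.

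**What to change.** - In Section 5.7, delete the condition on satisfactory results.
- In Sections 5.7 and 5.12, state that study success (41%) and the component comparisons are judged once, at 24 months.
- Label any 12-month submission as interim, with no success claim. Report IDE and OUS patients in it at the same timepoint, and do not set 12-month cumulative safety against 13.5%.
- Bring the one-year description of fusion in Section 5.2.1.A, the two submission sentences in 5.7, and the 12- and 24-month evaluation and the 24-month composite in 5.12 into agreement.

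The sponsor need not be obliged to file at 12 months whatever the results; it is enough that no success claim rests on that filing. If an early claim is wanted, the alternative is to pre-specify a 12-month analysis with its own criterion, decision rule and error control.

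The cost is a change of wording, made before results are seen. All 24-month visits are already planned. The small downside is losing the option of an early success claim.

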5.8 MISSING DATA

Incomplete information may be available for a subject for various reasons:

- Subject stopped participation in the study at its own request;
- Continuing the follow-up is not possible/subject lost to follow-up;

Subject stopped participation in the study at the Investigator's discretion.

In general, in cases where information will be available for a certain missing data point from a previous and from the next follow-up, an interpolation of the values shall be performed. Missing data from patients that were lost to follow-up will be handle by "last value carried forward" approach (*i.e.*, the last value obtained from a subject will be used for the analysis).

5.9 **PROCEDURES**

5.9.1 **PREOPERATIVE MANAGEMENT**

- a. The Investigator will select the subjects according to the inclusion and exclusion criteria, as described in Sections 5.3 and 5.4, respectively.
- b. The Investigator will be acquainted with the technique and instrumentation required for the procedure. Training will be provided by the Sponsor or its authorized representatives in accordance with the Training Protocol (**Appendix C**).
- c. The Investigator will be familiar with the Protocol of the clinical trial.
- d. Signed written Informed Consent must be obtained for all subjects.
- e. The patients shall be instructed to refrain from the use of NSAIDS for two weeks prior to surgery.
- f. All female subjects who are of child bearing age should present a negative beta-HCG blood (pregnancy) test or submit a signed statement that she is using at least one conventional contraceptive method and that to the best of her knowledge she is not pregnant. Such woman shall be informed of the risks involved in participating in the study while pregnant and cautioned to inform the study personnel if she becomes pregnant during the timeframe of the study.

Pre-procedure assessment will be conducted according to the outline provided in the Case Report Forms (CRFs) booklet.

Pre-procedure examination includes (refer also to Table 8 below):

- Demographic data
- > Full medical history, including concomitant medications

- Physical examination
- Neurological examination
- ➢ X-Ray evaluation

The results of the said examinations shall be recorded.

During the pre-operative session, the following forms shall be completed (refer also to **Table 9** below):

- > Pre-operative CRF
- Patient baseline questionnaires (Visual Analogue Scale (VAS, for back and leg pain assessment), Oswestry Disability Index (ODI), and 12-Item Short Form Health Survey (SF-12)

